Trial Design	
An observer-blind forearm-controlled clinical trial in 37 AD patients, wherein each participant will undergo 4 weeks treatment with crisaborole (2%) ointment on one forearm and betamethasone valerate (0.1%) cream on the other (twice daily application in each case and randomised site allocation). At the start of the study the skin of the test sites (forearms) will be clear of the signs of AD so that the investigation focuses on local adverse effects on the skin as opposed to anti-inflammatory effects (focus on local adverse effects and not clinical efficacy). The condition of the skin will be assessed before, during and after treatment.
	
Trial Participants	
Participants 18-65 years old with AD not currently undergoing, or requiring, active drug treatment.
	
Planned Sample Size	
A single cohort of 37 participants will be recruited with a target of 33 for completion (allowing for a 10% drop out rate)
	

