7.5.1 Randomization

Allocation of the treatments to the test sites (right/left forearm) will be randomised (to avoid site position-dependent artefacts) 1:1 using a randomization schedule (list) provided by the Statistical Services Unit. The list will be numbered using the unique participant randomization number, such that participant 001 will be dispensed products according to the first anatomical site allocation on the list and so on. The Sheffield Teaching Hospitals Pharmacy will undertake and document the randomization and label the IP's with the site of application upon issue to the site research facility team. Only the Pharmacy and study Statistician (SSU) will have access to the randomisation master list.

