2.2 Randomisation

Screening will take place either before or at the same visit as day 1. Those eligible to take part will be randomised on day 1 with each subject testing both treatments – one on each of the left or right lower volar forearm. The randomisation list will be provided by the SSU and the SSU will unblind the database after database lock. The interim analysis has been designed to be done on blinded data.

The pharmacy and a statistician (independent of the study statistician) will have access to the randomisation master list. Since only the research team assessing the study endpoints are blind to the treatment allocation and participants are all prescribed both treatments, no emergency unblinding arrangements are necessary.

2.3 Sample size:

The primary statistical analyses will compare the change in epidermal thickness from baseline to 28 days between treatments: betamethasone valerate cream vs crisaborole, utilising the within participant comparisons of left vs right forearm. Assuming that the change from baseline at day 28 in the betamethasone valerate group will be approximately $-4.44\mu\text{m}$ and a standard deviation of $5\mu\text{m}$ (for the change from baseline within each participant), to detect a reduction in this change of 80% to $-0.88\mu\text{m}$ in the crisaborole arm with 80% power, a parallel group study (one group for betamethasone valerate and one group for crisaborole) would require 33 participants in each group.

The study described here is comparing within participants (left vs right arm) rather than a parallel group (between participants) design, however it is assumed that this within patient comparison will have greater power than the parallel group design. This assumption is necessary because no information is available in the literature as to the standard deviation of the difference between change from baseline on the TCS arm and change from baseline on the crisaborole arm. Assuming that the correlation between these two 'change from baseline' measures will be greater than zero then the within participant comparisons can be assumed to have greater power than a parallel group design.

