7.1 Primary Analysis

The primary analysis of change in epidermal thickness over 28 days treatment will be estimated using a repeated measures mixed model with change from day 1 as the outcome, treatment, timepoint as factors together with a treatment by timepoint interaction, subject as a random effect and baseline as a covariate. The estimate of change from baseline to day 29 from this model will be the primary outcome, the estimate of change from day 1 to day 15 and change from day 29 to 57 will be secondary as described by in section 7.2.

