7.5 Multiplicity considerations

All analyses in this SAP will be carried out with a two sided 5% significance level.

Secondary analyses are considered to be exploratory and so no adjustment will be made for multiplicity.

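### The primary model's single, undefined baseline term can under-adjust the forearm contrast; splitting it into participant mean and forearm deviation is a nearly free improvement

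*SAP*

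**What the plan says.** SAP 7.1 models change in epidermal thickness from day 1 with treatment, timepoint and their interaction, plus "subject as a random effect and baseline as a covariate". The day-29 estimate from this model is the primary result. SAP 7.2 uses the same form for redness, TEWL and dryness.

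SAP 6.4 averages the triplicate OCT readings separately for each site and visit, so every participant has a left and a right day-1 value. The comparison is within person: SAP 2.3 describes it as "utilising the within participant comparisons of left vs right forearm", and Protocol 7.5.1 says "Allocation of the treatments to the test sites (right/left forearm) will be randomised (to avoid site position-dependent artefacts) 1:1".

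The SAP does not say whether baseline means the forearm's own value or the participant's mean. It names no covariance structure beyond the subject effect. Protocol 10.4.2 planned a paired analysis of change with no baseline covariate.

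**The concern.** The treatment effect is one forearm minus the other in the same person. Only the left-right difference at day 1 can remove noise from that contrast.

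- **If baseline is the participant mean**, it is identical for both forearms and drops out.
- **If baseline is the forearm value**, the model estimates one slope from two relations. Between people, baseline can be a fairly reliable trait, so change may depend on it only weakly. Between a person's two forearms, much of the day-1 difference may be measurement error, which reappears with opposite sign in the change, so that slope can be strongly negative. A pooled slope lies between the two and can correct the contrast too little.

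At stake is some precision on the primary endpoint of a trial with 33 planned completers, from data that are collected anyway.

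**Working it through.** **1. The plan's own figure.** Inputs from SAP 2.3, Protocol 10.1 and SAP 7.5: difference 3.55 µm, SD of change 5 µm, 80% power, two-sided 5%.

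n per group = 2(1.960 + 0.842)² × 5² / 3.55² = 392.6 / 12.60 = 31.2, so 32 by the normal formula. The t-test version gives 33 (power 0.811), which matches "would require 33 participants in each group". Dropout: 33 / 0.90 = 36.7, so 37. With 33 pairs and no baseline adjustment, power is 0.799, 0.917 and 0.977 for a correlation between the two changes of 0, 0.3 and 0.5. No baseline term enters, so this point leaves the sample size alone.

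**2. What a baseline term does to the contrast.** Let dX be the left-right difference at day 1 and dY the left-right difference in change at day 29. A forearm-level term with slope b turns the contrast into dY − b·dX, and

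Var(dY − b·dX) = V_min + (b − βW)² Var(dX),

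where βW is the within-person slope. Split baselines use b = βW. One forearm-level term uses b = w·βW + (1 − w)·βB, with βB the between-person slope and w a weight set by the variances. A participant-mean term gives b = 0.

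**3. Slopes, under assumptions.** Let u be the between-person variance, a the true left-right variance and m the measurement variance, with true change unrelated to true baseline. Then βW = −m/(a + m) and βB = −m/(2u + a + m). None of these variances is in the documents.

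**4. One case worked through.** SDs in µm: between-person 8, left-right 1, measurement 2.5, response 3.5, with response variance shared equally between person and forearm.

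- SD of change: √(3.5² + 2 × 2.5²) = √24.75 = 4.97, in line with the planned 5.
- βW = −6.25/7.25 = −0.86; βB = −6.25/135.25 = −0.05.
- Forearm-level variance of change: 6.125 + 12.5 = 18.63. After full adjustment: 18.63 − 6.25²/7.25 = 13.24.
- A REML fit of the SAP model (33 participants, days 15, 29 and 57, subject effect only) gave a pooled slope of −0.28. Variance ratio: 1 + (0.86 − 0.28)² × 7.25/13.24 = 1.18. The simulated ratio was also 1.18.
- Participant-mean term: 18.63/13.24 = 1.41 (simulated 1.40).

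**5. Five cases, same model, 2000 runs each.** The table gives the variance of the day-29 contrast relative to split baselines; the SE ratio is the square root.

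| SDs: between / left-right / measurement / response | Left-right baseline correlation, u/(u + a + m) | Forearm term: variance | Forearm term: SE | Participant-mean term: variance |
|---|---|---|---|---|
| 8 / 1 / 2.5 / 3.5 | 0.90 | 1.18 | 1.09 | 1.40 |
| 12 / 2 / 3.2 / 2 | 0.91 | 1.26 | 1.12 | 1.50 |
| 8 / 2 / 2.5 / 3.5 | 0.86 | 1.08 | 1.04 | 1.24 |
| 5 / 1 / 2.5 / 3.5 | 0.78 | 1.06 | 1.03 | 1.36 |
| 8 / 4 / 2 / 4 | 0.76 | 0.99 | 0.99 | 1.03 |

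A shorter rerun (200 runs per case) gave 0.99 to 1.27 for the forearm term.

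**6. A second set of assumptions.** Here the left-right baseline correlation was 0.3-0.9, the correlation of changes 0.3-0.7 and the noise share of left-right differences 0.5-1. Over nine cases of the SAP model, the SE ratio was about 1.00 to 1.04, and 1.11 when all left-right variation was noise. A day-29-only version, with noise share 0.5 and a correlation of changes from 0 to 0.7, gave 1.001 to 1.056. The single-term, split and unadjusted paired analyses all averaged about 3.5-3.6 for a true 3.55, so there was no sign of bias.

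**7. Sample-size equivalent.** 1 − 1/1.26 = 0.21, about a fifth, at the upper end.

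**The case against.** A single baseline covariate is conventional, and the one-term model is not worse than what the protocol planned: its SE was below that of the unadjusted paired analysis in every case examined. The gain is nil when true left-right differences are large relative to measurement error. The 26% case assumes that measurement noise makes up 2 × 3.2² = 20.5 of a change variance of about 24.5 (84%), although each reading averages three scans. All of this stands, and it makes the point an improvement and not an error.

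A reader might infer more than the documents support:

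- **That differences between people set most of the slope.** In the five tabulated cases the within-person weight was about 0.25 to 0.49. In the nine cases of step 6 it was 0.34 to 0.87, and at least 0.5 in eight. The documents do not settle which applies.
- **That the reported confidence interval will be too wide.** With only a subject effect, the model's own SE fell below the true one (for example 0.81 against 0.99), so the interval may be too narrow. That comes from the unspecified covariance between visits on the same forearm, a separate matter which the split does not cure.
- **That a quarter of the sample is lost.** That needs a variance ratio of 1.33 (1 − 1/1.33 = 0.25), which arises only if a forearm-within-subject effect is added. The SAP has none. Such a model reached an SE ratio of 1.23 in the all-noise extreme, and a day-29-only model 1.32.
- **That the secondary endpoints gain too.** Only thickness was simulated. The visual scores are coarse, and test sites must be clear of eczema at entry, so there may be little day-1 redness to split.

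**Conclusion.** The point holds as a free improvement, with moderate confidence. The mechanism follows from the two documents: two baselines per participant, one undefined term, and a within-person contrast. Under the participant-mean reading the contrast gets no adjustment. Under the forearm reading it can be under-adjusted.

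The size is conditional. For the forearm reading, the true SE of the day-29 contrast is usually 0-6% larger than with split baselines, and about 10-12% larger when measurement error dominates true left-right differences. In variance terms that is 0% to about 26%, or up to about a fifth of the sample. For the participant-mean reading the loss in the same five cases was larger (variance ratio 1.03 to 1.50), which is a further reason to define the term. All of these figures rest on assumed variances. SAP 2.3 itself says that the SD of the within-person difference is unknown.

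The documents support neither a bias in the treatment estimate nor a shortfall in the planned sample size.

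**What to change.** In SAP 7.1, keep the subject effect and replace the single baseline term with two covariates:

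1. the participant's mean day-1 epidermal thickness over both forearms;
2. the forearm's day-1 thickness minus that mean.

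The day-29 treatment contrast is then read from the model as already planned. Use the same pair of terms in the SAP 7.2 mixed models so that the specifications agree; no gain is claimed there.

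The cost is one sentence in the SAP and one extra model parameter, with no new data and no change to the sample size. The downside is essentially no gain if true left-right differences turn out to be large relative to measurement error. The change should be made before unblinding.

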7.2 Secondary Analysis

The analysis of three of the secondary endpoints will use a repeated measures mixed model with change from day 1 (to day 15, day 29, day 57) as the outcome, treatment, timepoint as factors together with a treatment by timepoint interaction, subject as a random effect and baseline as a covariate.

The model will be used to estimate the difference between treatment arms for the change from baseline to day 29.

If there is a significant difference observed in the change from baseline to day 29, then the change from day 1 to day 15, and the change from day 29 to day 57 will also be assessed. If there is no statistically significant difference in the change from baseline to day 29 then we will not test further timepoints.

Summary statistics will be presented for all timepoints.

This applies to:

- Change in epidermal thickness (change from day 1 to day 15, and from day 29 to day 57 as secondary endpoints)
- Change in redness/erythema
- Change in Trans-Epidermal Water Loss (TEWL)
- Change in visual skin dryness

The Change in TEWL_{ts20} after 28 days treatment will use an ANCOVA model with change from day 1 to day 29 as outcome, treatment as a factor, subject as a random effect and baseline as a covariate. The analysis of Natural Moisturising Factor after 28 days treatment (day 29) will

use a paired analysis (such as a t-test, depending on the distribution of the data) unless it is necessary to adjust for any covariates, in which case an ANCOVA will be used. If any of the above models do not fit satisfactorily or appear to be over fitted the analysis may be changed to look at change from baseline to day 29 and change from day 29 to 57 separately.

Since these analyses are exploratory, no adjustment for multiplicity will be made.

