6.2 Secondary endpoints

- Epidermal thickness measured by structural OCT during and after 28 days treatment:
 - Change in epidermal thickness (day 15 - day 1)
 - Change in epidermal thickness (day 57 - day 29)
- Erythema (visual redness) score during and after 28 days treatment:
 - Erythema score change from baseline (day 15, day 29, day 57)
- Objective redness as assessed with a Mexameter during and after 28 days treatment
 - Objective redness change from baseline (day 15, day 29 and day 57)
- Trans-Epidermal Water Loss during and after 28 days treatment
 - TEWL change from baseline (day 15, day 29, day 57)
- Skin barrier integrity after 28 days treatment:
 - Difference in TEWL_{ts20} between the two treatments (day 29)
- Visual skin dryness during and after 28 days treatment:
 - Dryness change from baseline (day 15, day 29, day 57)
- NMF at the end of treatment (quantified from superficial stratum corneum samples):
 - Difference between the two treatments (day 29)

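### For TEWL, both redness measures and dryness, SAP 7.2 follows up with day 29 to day 57, whereas SAP 6.2 and the analysis tables define the endpoint as day 57 minus day 1

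*SAP*

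**What the plan says.** SAP 6.2 defines the four outcomes by change from baseline:

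- TEWL: "TEWL change from baseline (day 15, day 29, day 57"
- Visual erythema: "Erythema score change from baseline (day 15, day 29, day 57"
- Mexameter: "Objective redness change from baseline (day 15, day 29 and day 57"
- Dryness: "Dryness change from baseline (day 15, day 29, day 57"

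Tables 14.2.2.2, 14.2.5.2, 14.2.6.2 and 14.2.7.2 in SAP 9, which hold the analyses of these outcomes, are titled to match: days 15, 29 and 57, each minus day 1.

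SAP 7.2 fits a repeated measures mixed model to change from day 1 at days 15, 29 and 57, with a treatment by timepoint interaction. The first comparison is the between-treatment difference at day 29. If it is significant, "then the change from day 1 to day 15, and the change from day 29 to day 57 will also be assessed"; if not, no further timepoints are tested. Should a model fit poorly, "the analysis may be changed to look at change from baseline to day 29 and change from day 29 to 57 separately". Summary statistics are shown at all timepoints. A note under Table 14.2.1.2 limits that table and the similar secondary tables to comparisons actually carried out, and points to SAP 7.2.

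Epidermal thickness is defined differently. SAP 6.2 lists "Change in epidermal thickness (day 57 - day 29", and SAP 7.1, SAP 7.2 and Table BDR1.3 agree with it.

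**The concern.** The rule in SAP 7.2 tests a different quantity from the endpoint in SAP 6.2. It suits epidermal thickness, but it is applied to four outcomes that are defined otherwise.

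Change from day 29 to day 57 measures what happens after stopping. Day 57 minus day 1 measures whether the arms still differ in their departure from baseline. Protocol 5 says the four-week washout is there to show how quickly the skin returns to baseline, and the first contrast alone does not answer that. If a treatment difference at day 29 were still fully present at day 57, the follow-up contrast named in SAP 7.2 would be expected to show nothing. A reader could then take a null result as reassurance about the post-treatment period.

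There is a practical gap as well. Two programmers working from this SAP could reasonably fill the day-57 row of the four analysis tables differently.

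**Working it through.** The plan gives no figure for this contrast, so the check is a comparison of sections followed by short algebra.

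**1. Where each contrast appears (TEWL, visual erythema, Mexameter redness, dryness)**

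| Contrast | SAP 6.2 endpoint | Comparison named in SAP 7.2 | Analysis table titles |
|---|---|---|---|
| Day 29 − day 1 | yes | yes, first | yes |
| Day 15 − day 1 | yes | yes, if day 29 is significant | yes |
| Day 57 − day 1 | yes | no, though it is a model outcome | yes |
| Day 57 − day 29 | no | yes, if day 29 is significant; also in the fallback | no |

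The first two rows agree throughout. The last two are mirror images: one contrast has an endpoint and a table but no named comparison, and the other has a named comparison but no endpoint or table.

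**2. What each contrast estimates**

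Let D29 and D57 be the between-arm differences in change from day 1 at days 29 and 57. Then day 57 − day 1 estimates D57, and day 57 − day 29 estimates D57 − D29.

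| Scenario | D57 | Day 57 − day 1 | Day 57 − day 29 |
|---|---|---|---|
| Full persistence | D29 | D29 | 0 |
| Half recovery | D29/2 | D29/2 | −D29/2 |
| Full recovery | 0 | 0 | −D29 |

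At the two extremes, one contrast is null exactly where the other carries the whole effect.

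**3. Precision under the stated model**

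Take the SAP 7.2 model with subject as the only random effect, balanced data, residual SD σ, n = 33 completers (SAP 2.1), and the baseline covariate ignored. The subject effect cancels between arms, so:

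- SE(day 57 − day 1) = σ√(2/n) = σ√(2/33) = 0.246σ
- SE(day 57 − day 29) = σ√(4/n) = σ√(4/33) = 0.348σ

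The ratio is √2, so under this model the unnamed contrast is the more precise of the two. σ is unknown for these outcomes and is left as a symbol.

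**4. Is day 57 − day 1 available?**

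Yes, from the joint model: it is the treatment effect at the day-57 level of the interaction, with its own CI. Under the fallback, days 1 to 29 and days 29 to 57 are analysed separately. No single fit then returns an interval for day 57 − day 1, and combining the two intervals would need their covariance.

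**The case against.** The best reply is that nothing is really lost. The model in SAP 7.2 already has change from day 1 at day 57 as an outcome, the table titles ask for it, descriptive changes from day 1 are planned (for example Table 14.2.2.1), and Protocol 10.4.3 says results will come with confidence intervals. The secondary analyses are exploratory, and SAP 2.4 leaves analysis decisions to blind review. Most of this stands and sets the severity. It does not settle which contrast SAP 7.2 intends, and the model argument fails under the fallback.

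Some stronger readings are tempting, but the documents do not support them:

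- **That the table note removes day 57 − day 1 from the outputs.** A literal reader could infer this. Because SAP 7.2 makes later comparisons conditional on day 29, the note more naturally refers to that condition.
- **That rejection rates can be attached.** The only effect size and SD given (a 3.55 µm difference and an SD of 5 µm, Protocol 10.1) are for epidermal thickness. They do not transfer to TEWL, the Mexameter or short visual scales (0 to 3 and 0 to 4). Paired t-test rates would also not match the planned mixed model.
- **That SAP 7.2 miscounts its endpoints.** It says "The analysis of three of the secondary endpoints will use a repeated measures mixed model" and lists four bullets. Thickness is already modelled in SAP 7.1, and Protocol 4.5 and 10.4.3 treat redness/erythema as one item, so three can be right.
- **That the opening of SAP 7 and the interim recovery plot in SAP 7.7 add evidence.** The opening names no day. The day 29 to day 57 plot follows on from epidermal thickness and carboxylate, which are not among these four outcomes.
- **That epidermal thickness has the same fault.** Its endpoint and analysis text agree; only the titles of Tables 14.2.1.1 and 14.2.1.2 differ.

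**Conclusion.** The inconsistency is real and confined to TEWL, visual erythema, Mexameter redness and dryness. SAP 6.2 and the analysis table titles define the post-treatment comparison against day 1; the conditional rule and the fallback in SAP 7.2 name only day 29 to day 57. The defined contrast is available from the joint model but unnamed, and the named contrast has no endpoint or table.

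The consequence can be stated in direction only: full persistence is invisible to day 57 − day 29, and full recovery shows as no difference on day 57 − day 1. That follows from the definitions. The √2 precision ratio also assumes a balanced random-intercept model. No rate or effect size can be given for these outcomes.

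Severity is low. The primary day-29 comparison and the sample size are untouched and the affected analyses are exploratory. It is still worth correcting before unblinding, because it governs what can be concluded about return to baseline and a later choice could look data-driven.

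**What to change.** In SAP 7.2, keep the day-29 condition. After it, name the day 57 − day 1 between-treatment difference with 95% CI, from the same fitted model, as the contrast matching the SAP 6.2 endpoint for TEWL, visual erythema, Mexameter redness and dryness. State that it is also estimated if the fallback is used.

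If day 29 to day 57 is kept for these outcomes, label it a supporting recovery contrast and add a row for it to Tables 14.2.2.2, 14.2.5.2, 14.2.6.2 and 14.2.7.2. State that the note under Table 14.2.1.2 refers to the day-29 condition.

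For epidermal thickness, keep day 57 − day 29 and align the title of Table 14.2.1.2 with SAP 6.2, 7.1 and 7.2.

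A non-significant day 57 − day 1 difference should be read through its interval, not as proof of return to baseline.

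The cost is some SAP wording and, if the supporting contrast is kept, one row in each of four tables. No new data are needed, and no new model unless the fallback is used, when day 57 − day 1 needs its own fit. The downside is one extra unadjusted exploratory contrast per outcome.
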